5.6. Prior and Concomitant Medications

Concomitant medications taken within 30 days prior to screening, up to and including 30 days after the last dose of study drug, need to be recorded in the source documents and electronic case report form(s) (eCRFs).

The following medications are prohibited during the screening period and for a minimum of 28 days prior to the Day 1 visit through the end of treatment:

- Hematologic stimulating agents (e.g., erythropoiesis-stimulating agents (ESAs); granulocyte colony stimulating factor (G-CSF); thrombopoietin (TPO) mimetics)
- Chronic use of systemic immunosuppressants including, but not limited to, corticosteroids (prednisone equivalent of > 10 mg/day for > 2 weeks), azathioprine, or monoclonal antibodies (e.g., infliximab)
- Investigational agents or devices for any indication
- Drugs disallowed per prescribing information of REBETOL[®] for GT-3 subjects only

Concomitant use of certain medications or herbal/natural supplements (inhibitors or inducers of drug transporters i.e., P-gp) with study drug(s) may result in PK interactions resulting in increases or decreases in exposure of study drug(s). **Examples of representative medications which are prohibited from 21 days prior to Day 1 through the end of treatment are listed below (Table 5-1). In addition, the use of amiodarone is prohibited from 60 days prior to Baseline/Day 1 through the end of treatment.**

Table 5-1. Disallowed and Concomitant Medications to be Used with Caution

Drug Class	Agents Disallowed	Use with Caution
Acid Reducing Agents ^a		Proton- Pump Inhibitors, H2-Receptor Antagonists, Antacids
Anticonvulsants ^c	Phenobarbital, Phenytoin, Carbamazepine, Oxcarbazepine	
Antimycobacterials ^c	Rifabutin, Rifapentine, Rifampin	
Cardiac Medications	Amiodarone ^e	Digoxin ^b , Dabigatran ^b
Herbal/Natural Supplements ^c	St. John's Wort, Echinacea, Milk thistle (i.e., silymarin), Chinese herb sho-saiko-to (or Xiao-Shai-Hu-Tang)	
HMG-CoA Reductase Inhibitors ^d	Rosuvastatin	Atorvastatin, Simvastatin, Pravastatin, Pitavastatin, Fluvastatin, Lovastatin

- a It is recommended to separate antacid and LDV/SOF FDC administration by 4 hours. H2-receptor antagonists may be administered simultaneously with or staggered from LDV/SOF FDC at a dose that does not exceed doses comparable to famotidine 40 mg twice daily. Proton-pump inhibitor doses comparable to omeprazole 20 mg can be administered simultaneously with LDV/SOF FDC or up to 2 hours after taking LDV/SOF FDC. Proton-pump inhibitors should not be taken before LDV/SOF FDC.
- b May result in an increase in the concentration of study drug and/or concomitant medications. Co-administration of LDV/SOF FDC with digoxin or dabigatran may increase the concentration of digoxin or dabigatran. Caution is warranted and therapeutic concentration monitoring of digoxin or clinical monitoring of dabigatran is recommended when co-administered with LDV/SOF FDC.
- c May result in a decrease in the concentrations of study drug.
- d Use with study drug may result in an increase in the concentration of the HMG-CoA Reductase Inhibitors. Monitor for signs and symptoms of muscle weakness or myopathy, including rhabdomyolysis.
- e May result in symptomatic bradycardia. Mechanism is not currently known. The use of amiodarone is prohibited from 60 days prior to Baseline/Day 1 through the end of treatment.

Medications for disease conditions **excluded** from the protocol (e.g., active cancer, transplantation) are not listed under this Concomitant Medication section and are disallowed in the study.

6. STUDY PROCEDURES

All subjects will complete screening, on-treatment, and post-treatment assessments. Screening assessments will be completed within 28 days of the Day 1 visit. The end of study will occur at the 24-week Post-Treatment visit. The schedule of assessments is described below.

Information on the specific laboratory parameters to be measured and clinical assessments to be performed are provided in Section 6.6.

6.1. Subject Enrollment

Each candidate's parent or legal guardian must sign an Informed Consent Form prior to the conduct of any screening procedures. Each study candidate who has the ability to read and write must sign an Assent Form, as required by IRB/IEC/local requirements, prior to the conduct of any study procedures. Screening evaluations will be used to determine the eligibility of each candidate for study enrollment. Candidates who fail to meet eligibility criteria by screening evaluations may be re-screened once ≥ 30 days after the initial screen if there is a reasonable expectation that the candidate will be eligible after repeat screening.

6.2. Screening Assessments

6.2.1. Screening Visit (Day -28 to Day 0)

Subjects will complete all screening assessments within 28 days of the Day 1 visit. The screening window can be extended to 42 days for subjects requiring additional HCV GT testing or for extenuating circumstances.

The following procedures will be performed and documented:

- Written informed consent from parent or legal guardian and assent from subject, if applicable (see above)
- Medical history, including:
 - Hepatitis C history
 - Hepatitis C treatment history
 - Family history (including height of parents, if known)
 - Liver biopsy results (if available)
- Complete physical examination
- Vital signs (temperature, blood pressure, pulse, respiratory rate) and body weight and height

- Obtain blood samples for tests as listed in Section 6.6.1:
 - Hematology
 - Chemistry
 - Coagulation tests
 - HCV RNA
 - Determination of HCV viral GT and subtype
 - HCV antibody, HIV 1/2 antibody, HBV surface antigen (HBsAg), HBV surface antibody (HBsAb), HBV core antibody (HBcAb), and HAV antibody
 - HbA_{1c}
 - TSH
 - IL28B
 - Serum β -hCG pregnancy test for females of childbearing potential only
 - Alpha fetoprotein (AFP)
 - Alpha-1 anti-trypsin (ATT)
- Obtain urine sample for:
 - Urinalysis
 - Urine Drug Screen
- Review of concomitant medications
- Ask subject and/or parent/legal guardian if the subject is able to swallow and tolerate taking pills.
- Review of all inclusion and exclusion criteria
- Perform LDV/SOF FDC swallowability assessment, as applicable

Subjects meeting all of the inclusion criteria and none of the exclusion criteria will return to the clinic for the Day 1 visit assessments.

6.3. PK Lead-in: Treatment Assessments

6.3.1. Day 1

After confirmation of eligibility has been evaluated, the following tests and procedures must be completed prior to enrollment and dosing/dispensing on Day 1:

- Perform complete physical examination
- Tanner Pubertal Stage Assessment
- Vital signs, including body weight and height measurements
- A single X-ray of the left wrist, hand, and fingers for Bone Age Assessment
- Assessment of AEs and concomitant medications
- Pregnancy prevention counseling including partner pregnancy prevention for male participants (all subjects \geq 12 years of age and subjects $<$ 12 years of age at the discretion of the Investigator based on subject's pubertal status)
- Obtain blood samples for:
 - Hematology
 - Chemistry
 - Coagulation tests
 - HCV RNA
 - Viral sequencing (archive)
 - HBV DNA testing for subjects HBcAb positive at Screening
 - PPD
- Obtain urine samples for the following procedures:
 - Urinalysis
 - β -hCG pregnancy test for females of childbearing potential only
- Subject completes quality of life survey: Subject is to review questionnaire with a parent/guardian and write/mark answers directly onto the questionnaire.

6.3.1.1. Drug Administration

- Dispense study drug(s) as directed by the IWRS
- Instruct the subject on the packaging, storage and administration of study drug
- Perform LDV/SOF FDC swallowability assessment (for subjects administered LDV/SOF FDC in tablet form only if not previously completed at screening). Observe the subject taking the first dose of study drug (with or without food) and record the time of first dose
- Subjects will be administered a dosing diary with instructions.

6.3.2. Day 3

The following procedures/assessments are to be completed on Day 3:

- Perform a symptom-directed physical examination as needed
- Vital signs, including body weight and height
- Assessment of AEs and concomitant medications
- Review medication compliance with subject and/or subject's parent/guardian
- Obtain blood samples for:
 - Hematology
 - Chemistry
 - HCV RNA
 - Viral sequencing (archive)
- Review subject dosing diary

6.3.3. Day 10 – Intensive PK

The Day 10 Intensive PK visit should occur on the protocol-specified visit date based on the Day 1 visit. For the purposes of scheduling, the Day 10 Intensive PK visit may be performed within +3 days of the protocol-specified visit date (subjects will continue daily dosing through the Intensive PK Visit).

Subjects should come in a fasted state for the Day 10 Intensive PK visit (i.e., no food or drink except water at least 8 hours prior to the Day 10 Intensive PK visit). Subjects and/or parents/guardians should be instructed that the Day 10 dose of LDV/SOF FDC must **not** be taken until the evaluations listed below are completed.

If the subject has already dosed prior to the Day 10 clinic visit or is **not** in a fasted state, the Day 10 intensive PK assessments must not be completed. The subject and/or parents/guardians should be instructed to return in a fasted state within 3 days (Days 11, 12, or 13) for the intensive PK visit.

If dosing non-compliance is identified as per subject dosing diary and study drug count on or prior to the Day 10 visit, the Day 10 intensive PK assessments must not be completed. The subject and/or parents/guardians should be counseled regarding proper dosing and be scheduled to return for the Day 10 intensive PK visit no sooner than 3 days following compliant dosing and no later than Day 14 (i.e., return on Day 13 or Day 14). If dosing non-compliance is due to an AE, consultation with the Gilead Medical Monitor is required regarding the potential of rescheduling the Day 10 intensive PK visit.

In both scenarios described above, the subject and/or parents/guardians should be reminded not to take the LDV/SOF FDC prior to arriving at the clinic on the day of the re-scheduled intensive PK visit. All Day 10 intensive PK assessments listed below should be completed when the subject returns.

The following evaluations are to be completed at the Day 10 Intensive PK visit:

- Perform a symptom-directed physical examination
- Vital signs, including body weight and height
- Assessment of AEs and concomitant medications
- Perform study drug accountability
- Review Subject Dosing Diary
- Review medication compliance with subject and/or parent/guardian.
- Obtain urine samples for the following procedures:
 - Urinalysis
 - Urine pregnancy test (females of childbearing potential only). If the urine pregnancy test is positive, the Intensive PK sampling will not be completed. The positive result will be confirmed with a serum pregnancy test.
- Obtain blood samples for the following laboratory analyses:
 - Hematology
 - Chemistry

- Coagulation tests
- HCV RNA
- Viral sequencing (archive)
- Perform intensive PK sampling:
 - Blood samples will be collected at 0 (predose, ≤ 30 minutes prior to dosing). After collection of the predose sample, subjects will be provided a standardized meal. Within 5 minutes after consuming the standardized meal, subjects will be dosed with LDV/SOF FDC per dosing requirements.
 - Post-dose blood samples will be collected as follows:
 - For Cohorts 1 and 2: 0.5, 1, 2, 3, 4, 5, 8, and 12 hours post-dose (with predose also serving as $t = 24$).
 - For Cohort 3 only: 0.5, 2, 4, 8, and 12 hours post-dose (with predose also serving as $t = 24$).
 - Subjects will be restricted from food intake until after collection of the 4-hour post dose blood sample, except for subjects in Cohort 3. Please also refer to the PK manual for details about standardized meals and PK sample processing instructions.

After completing the Day 10 intensive PK visit subjects will then continue to the Week 2 visit in Treatment Phase (described in Section 6.4.2) with no interruption in dosing.

6.4. Treatment Phase: Treatment Assessments

6.4.1. Day 1

After confirmation of eligibility has been evaluated, the following tests and procedures must be completed prior to enrollment and dosing/dispensing on Day 1:

- Perform complete physical examination
- Tanner Pubertal Stage Assessment
- Vital signs, including body weight and height measurements
- A single X-ray of the left wrist, hand, and fingers for Bone Age Assessment
- Review of AEs and concomitant medications

- Pregnancy prevention counseling including partner pregnancy prevention for male participants (all subjects ≥ 12 years of age and subjects < 12 years of age at the discretion of the Investigator based on subject's pubertal status).
- Obtain blood samples for:
 - Hematology
 - Chemistry
 - Coagulation tests
 - HCV RNA
 - Viral sequencing (archive)
 - HBV DNA testing for subjects HBcAb positive at Screening
 - PPD 
- Obtain urine sample for:
 - Urinalysis
 - β -hCG pregnancy test for females of childbearing potential only
- Subject completes quality of life survey: Subject is to review questionnaire with a parent/guardian and write/mark answers directly onto the questionnaire
- Perform LDV/SOF FDC swallowability assessment (for subjects administered LDV/SOF FDC in tablet form only if not previously completed at screening)
- Perform LDV/SOF FDC oral granules palatability assessment, for Treatment Group 2 subjects from 3 to < 6 years of age, as applicable.

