6.6.12. Quality of Life Survey (PedsQL™)

The **PedsQL™** Pediatric Quality of Life Inventory V4.0 Short Form (SF15) will be completed at Day 1, End of Treatment, Early Termination (if applicable), 12-Week Post-Treatment, and 24-Week Post-Treatment visits.

The **PedsQL™** has separate survey instruments administered by age group, including the Teen Report (ages 13-18), Child Report (ages 8-12), Young Child Report (ages 5-7), and Toddlers (ages 2-4). Each survey accompanied by the respective parent proxy survey will be administered to the subject and their parent/legal guardian (with the exception of the Toddlers Report which will only be completed by the parent/legal guardian) for the current age group at the time of survey administration.

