Appendix Table 2. Treatment Phase: Screening and On-Treatment Study Visits

	Screening ^c (-28 days)	Day 1 ^c	Visit identified by on-treatment study week								Early Termination
			1 ^c	2	4	8	12	16 ^k	20 ^k	24 ^k	
Clinical Assessments											
Informed Consent / Assent	X										
Determine Eligibility	X	X									
Medical History	X ⁱ										
Complete Physical Examination	X	X					X ^j			X	X
Symptom-Directed Physical Examination			X	X	X	X	X ^k	X	X		
Tanner Pubertal Stage Assessment		X					X ^j			X	X
Vital Signs ^a	X	X	X	X	X	X	X	X	X	X	X
Bone Age Assessment		X									
AEs and Concomitant Medications	X	X	X	X	X	X	X	X	X	X	X
Pregnancy Prevention Counseling ^g		X					X ^j			X	X
LDV/SOF FDC Swallowability Assessment	X	X ^h									
Quality of Life Survey ^e		X					X ^j			X	X
Review of Study Medication Compliance					X	X	X	X	X	X	X
Study Drug Dispensing ^b		X			X	X	X ^k	X	X		
Palatability Assessment of Oral Granules as applicable		X									
Laboratory Assessments											
Hematology, Chemistry, Coagulation	X	X	X	X	X	X	X	X	X	X	X
HCV RNA	X	X	X	X	X	X	X	X	X	X	X
Viral Sequencing ^d		X	X	X	X	X	X	X	X	X	X
Serum or Urine Pregnancy Testing ^l	X	X			X	X	X	X	X	X	X
PPD											
Urinalysis	X	X									

	Screening ^c (-28 days)	Day 1 ^c	Visit identified by on-treatment study week								
			1 ^c	2	4	8	12	16 ^k	20 ^k	24 ^k	Early Termination
Urine Drug Test	X										
HCV Genotyping, IL28B	X										
HCV antibody, HIV antibody, HBs antigen, HBs antibody, HBc antibody, and HAV antibody	X										
HbA1c	X										
TSH	X						X ^j			X	X
Alpha fetoprotein, Alpha-1 anti-trypsin	X										
HBV DNA ^m		X			X	X	X	X	X	X	X
Single PK collected at any time point			X	X			X	X	X	X	X
Single PK Sample collected between 15 minutes to 4 hours post-dose ⁿ					X	X					

PPD

- a Vital signs include blood pressure, pulse, respiratory rate and temperature, and body weight and height
- b The IWRS will provide direction on the specifics of each subject's study drug dispensing.
- c Subjects rolling over from PK Lead-in phase will not be required to repeat screening, Day 1 or Week 1 visits during the on Treatment Phase
- d Plasma samples will be collected and stored for potential HCV sequencing and other virology studies
- e Quality of life survey will be completed by all subjects if a site is approved to use the survey. Subject is to review questionnaire with a parent/guardian and write/mark answers directly onto the questionnaire.
- f **PPD**

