Appendix 3. PedsQL™ Score Calculation Algorithms

The **Parent Report for Toddlers** (ages 2-4) and the **Child & Parent Reports for Young Children** (ages 5-7), **Children** (ages 8-12) and **Teens** (ages 13-18) of the **PedsQL™ 4.0 SF15** Generic Core Scales are composed of 15 items comprising 4 dimensions.

DESCRIPTION OF THE SF15 QUESTIONNAIRE:

Dimensions	Number of Items	Cluster of Items	Reversed Scoring	Direction of Dimensions
Physical Functioning	5	1-5	1-5	Higher scores indicate better HRQOL
Emotional Functioning	4	1-4	1-4	
Social Functioning	3	1-3	1-3	
School Functioning	3	1-3	1-3	

SCORING OF DIMENSIONS:

Item Scaling	5-point Likert scale from 0 (Never) to 4 (Almost always) 3-point scales: 0 (Not at all), 2 (Sometimes) and 4 (A lot) for the Young Child self-report
Weighting of Items	No
Extension of the Scoring Scale	Scores are transformed on a scale from 0 to 100
Scoring Procedure	
Step 1: Transform Score Items are reversed scored and linearly transformed to a 0-100 scale as follows: 0=100, 1=75, 2=50, 3=25, 4=0.
 
Step 2: Calculate Scores Score by Dimensions:
 
 • If more than 50% of the items in the scale are missing, the scale scores should not be computed, • Mean score = Sum of the items over the number of items answered. 
Psychosocial Health Summary Score = Sum of the items over the number of items answered in the Emotional, Social, and School Functioning Scales. Physical Health Summary Score = Physical Functioning Scale Score Total Score: Sum of all the items over the number of items answered on all the Scales.

Interpretation and Analysis of Missing Data	If more than 50% of the items in the scale are missing, the Scale Scores should not be computed.

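### Every visit list that includes the PedsQL has the child go through it with a parent, which conflicts with the separate child and proxy forms and with the parent-only form for ages 2-4

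*Protocol*

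**What the plan says.** Seven visit lists in the protocol include the survey: 6.3.1, 6.4.1, 6.4.4, 6.4.7, 6.4.9, 6.5.2 and 6.5.3. In 6.4.1 the bullet names the subject as the one who fills in the survey and gives this direction: "Subject is to review questionnaire with a parent/guardian and write/mark answers directly onto the questionnaire". The other six carry the same instruction. The footnotes to the three procedures tables in protocol Appendix 2 repeat it, adding "Quality of life survey will be completed by all subjects" on condition that the site is approved to use it. SAP Appendix 1 copies these footnotes.

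Protocol 6.6.12 describes the instrument differently. There are four age versions: Toddlers (2-4), Young Child (5-7), Child (8-12) and Teen (13-18). On who answers, the general rule is "Each survey accompanied by the respective parent proxy survey will be administered to the subject and their parent/legal guardian". The youngest version is then carved out as the "Toddlers Report which will only be completed by the parent/legal guardian". SAP Appendix 3 agrees: it lists only a parent report for toddlers, then "Child & Parent Reports for Young Children" and the same pairing for the two older groups.

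Protocol 9.7 plans summaries of the survey per visit, for each age group and pooled. It does not say whether self-report and proxy scores are kept apart.

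**The concern.** Collecting a self-report and a proxy report on the same child is useful because two people give their own views. Here the child is told to go through the questionnaire with the person who would normally supply the proxy rating. The instruction is not confined to young children who need help with reading; it applies equally to a 17-year-old. Nothing in either document asks for independent completion, limits the help a parent may give, or records who answered.

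For 3- and 4-year-olds the problem is different. No self-report form exists at that age, yet the visit lists have the subject mark the answers.

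At stake is what a score labelled as child-reported means. If it is not recorded who answered, this cannot be recovered once the data are in.

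**Working it through.** The plan gives no figure on this point and none is needed. The check is a comparison of text.

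1. **Where the instruction stands.** Section 6.6.12 schedules the survey at Day 1, end of treatment, early termination, and post-treatment Weeks 12 and 24. In the visit lists these are Day 1 (6.3.1, 6.4.1), end of treatment (6.4.4, 6.4.7), early termination (6.4.9) and post-treatment (6.5.2, 6.5.3): 2 + 2 + 1 + 2 = 7. All seven carry the instruction. None mentions the proxy form or the parent-only exception. The other visits (screening, Day 3, Day 10, Weeks 1, 2, 4, 8, 16 and 20, Week 12 of the 24-week regimen, and post-treatment Week 4) have no survey, so the point does not extend to them. With three protocol footnotes and three SAP footnotes, the sentence stands in 7 + 3 + 3 = 13 places.

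2. **The two descriptions side by side.**

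| Age at survey | Protocol 6.6.12 and SAP Appendix 3 | Visit lists and footnotes | Result |
|---|---|---|---|
| 3-4 | Parent form only | Subject marks answers after review with parent | Contradiction on who completes the form |
| 5-7 | Young Child form plus parent proxy | Same instruction; proxy not mentioned | Child form not independent of proxy |
| 8-12 | Child form plus parent proxy | Same | Same |
| 13 to < 18 | Teen form plus parent proxy | Same | Same |

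The row for ages 3-4 matters because inclusion criterion 2 admits children from age 3. SAP Appendix 3 also gives the Young Child self-report its own three-point response scale, so the scoring treats self-report as a form distinct from the proxy.

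3. **Who is affected.** The footnotes restrict the survey to sites approved to use it. The documents do not say how many sites that is, so the share of subjects is unknown.

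4. **What can be said about bias in change.** Write the child's recorded score at a visit as the child's own score plus a shift *b* due to joint review. Then recorded change = own change + (*b* after treatment − *b* at Day 1). The same instruction applies at Day 1, so a constant shift gives *b* − *b* = 0 and drops out of the change. Only a shift that differs between visits biases it, and that difference could have either sign. Neither document gives any information on *b*, so no size or direction follows.

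5. **How the data are used.** The PedsQL is not among the primary, key or secondary endpoints in protocol 9.1.2 and 9.1.3. Protocol 9.7 plans summaries, and SAP 3.5.1 adds a carry-forward rule at post-treatment Week 24. No analysis of child-parent agreement appears in the readable text. SAP 6.3 is redacted, so whether the two reports are summarised separately cannot be determined.

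**The case against.** The strongest reply is that the visit bullets are shorthand. The opening of protocol Section 6 sends the reader to 6.6 for details of the assessments, and 6.6.12 sets out the forms correctly. Reviewing a questionnaire with a parent may mean no more than going over its wording, which a child of 5 to 7 may need, and the text has the subject mark the answers. At ages 3-4 there is no self-report score to distort. The measure is descriptive and used only at approved sites.

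Much of this stands, and it limits the weight of the point. It does not remove the conflict. The bullet is an explicit instruction at each visit, with no limit by age or purpose, and the footnotes state it without an age exception. A pointer to 6.6 does not cancel it, and staff working from a visit list would follow the list.

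A reader might infer more: that the self-report is contaminated, and that parents who know the HCV RNA result pull it in a favourable direction after treatment. The documents do not support this. They show that joint review is instructed, not that answers are agreed jointly. Section 3.3 makes HCV RNA known to the investigator and sponsor and does not say what families are told. A constant influence would cancel from change.

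**Conclusion.** The conflict is real and is not resolved elsewhere in the readable text. At approved sites, following the visit lists as written allows the parent's view into the child's report from age 5, so that report is not independent of the proxy. For ages 3-4 the documents give contradictory instructions on who completes the form. The extent is all seven visit lists that include the survey and all six table footnotes. No bias in points, and no effect on child-parent agreement, can be stated from the documents.

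The point is minor: the readable text plans only descriptive summaries, and no primary, key or secondary endpoint depends on it. The conclusion assumes that site staff follow the visit lists as written and that no site instruction outside these documents already separates the respondents.

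**What to change.** In the seven visit lists, the footnotes to the three tables in protocol Appendix 2 and the copied footnotes in SAP Appendix 1, replace the sentence with wording to this effect: from age 5 the child completes the child form and the parent or guardian completes the proxy form, separately and without discussing the answers; for ages 2-4 only the parent form is completed; any reading help given to a young child is recorded on the form. Age is taken at the time of each survey, as 6.6.12 already provides.

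State in protocol 9.7 and the SAP that child and parent scores are summarised separately, unless the redacted SAP section already does so.

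The cost is the change of wording, one extra entry on the form, and a few more minutes for the youngest self-reporters. No new questionnaire is needed, and treatment and the primary analyses are untouched.
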